6.8 Treatment After the End of the Study

At the end of the study, the investigator should ensure that subjects continue to receive appropriate standard of care to treat the condition under study. In addition, for subjects who continue to demonstrate clinical benefit and who elect to enroll, BMS will continue to provide study treatment via Protocol IM011074, which is an LTE of the current study. Participation in IM011074 is not required for participation in this study, however.

BMS reserves the right to terminate access to BMS-supplied study treatment if any of the following occur: a) the study is terminated due to safety concerns; b) the development of BMS-986165 is terminated for other reasons, including but not limited to lack of efficacy and/or not meeting the study objectives; c) the subject can obtain medication from a government sponsored or private health program. In all cases BMS will follow local regulations

7 DISCONTINUATION CRITERIA

7.1 Discontinuation from Study Treatment

Subjects MUST discontinue the IP (and non-IP at the discretion of the investigator) for any of the following reasons:

- A subject requests to stop study treatment. Subjects who request to discontinue study treatment will remain in the study and must continue to be followed for protocol-specified follow-up procedures. The only exception to this is when a subject specifically withdraws consent for any further contact with him/her or persons previously authorized by subject to provide this information
- Any clinical AE, laboratory abnormality, or intercurrent illness that, in the opinion of the investigator, indicates that continued participation in the study is not in the best interest of the subject
- Termination of the study or a specific dose group (for subjects receiving that dose) by BMS
- Loss of ability to freely provide consent through imprisonment or involuntary incarceration for treatment of either a psychiatric or physical (eg, infectious disease) illness
- Unblinding of a subject's treatment assignment for any reason (emergency or nonemergency)
- Pregnancy
- Abnormal liver tests suggestive of drug-induced liver injury (DILI) as defined in [Section 8.3.8](#) or if the investigator believes that it is in the best interest of the subject.

Refer to the Schedules of Activities ([Section 1.3](#)) for data to be collected at the time of treatment discontinuation and follow-up and for any further evaluations that can be completed.

In the case of pregnancy, the investigator must immediately notify the [REDACTED] medical monitor or designee of this event. In the event a normal healthy female subject becomes pregnant during a clinical trial, the study treatment must be discontinued immediately. In most cases, the study treatment will be permanently discontinued in an appropriate manner (eg, dose tapering if necessary for subject safety). Please call the [REDACTED] medical monitor within 24 hours of awareness of the pregnancy. If the investigator determines a possible favorable benefit/risk ratio that warrants continuation of study treatment, a discussion between the investigator and the [REDACTED] medical monitor must occur.

All subjects who discontinue study treatment should comply with protocol-specified follow-up procedures as outlined in [Section 1.3](#). The only exception to this requirement is when a subject withdraws consent for all study procedures including post-treatment study follow-up or loses the ability to consent freely (ie, is imprisoned or involuntarily incarcerated for the treatment of either a psychiatric or physical illness). Subject replacement is not permitted.

If study treatment is discontinued prior to the subject's completion of the study, the reason for the discontinuation must be documented in the subject's medical records and entered on the appropriate eCRF page.

Subjects who discontinue study treatment will remain in the study for continued follow-up.

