| Procedure | Week 28 D197 (±3 d) | Week 32 D225 (±3 d) | Week 36 D253 (±3 d) | Week 40 D281 (±3 d) | Week 44 D309 (±3 d) | Week 48 D337/EOT (±3 d) | FP (28 days after EOT) ^a | Notes |
|--|---------------------------|---------------------------|---------------------------|---------------------------|---------------------------|-------------------------------|---|--|
| Safety Assessments | | | | | | | | |
| Complete PE | | X | | | | X | | General, head, eyes, ears, nose, throat, neck, cardiovascular, lungs, abdominal, extremities, neurologic, psychiatric, skin, musculoskeletal |
| Targeted PE | X | | X | X | X | | X | General, eyes, throat, cardiovascular, lungs, abdominal, extremities, skin, musculoskeletal, and others as clinically indicated |
| Body weight | X | X | X | X | X | X | X | |
| Vital signs | X | X | X | X | X | X | X | See note in Table 1 . |
| Electrocardiogram | | X | | | | X | | See note in Table 1 . |
| Concomitant medication use | X | X | X | X | X | X | X | |
| Monitor for AEs and SAEs | X | —————→ | | | | | X | |
| Laboratory Tests | | | | | | | | See note in Table 1 . |
| Hematology, chemistry, urinalysis, coagulation | X | X | X | X | X | X | X | |
| Fasting lipid panel | | X | | | | X | | |
| Fasting plasma glucose | | X | | | | X | | |
| Pregnancy test (WOCBP only) | X | X | X | X | X | X | X | See note in Table 1 . |
| Spot urine for protein creatinine ratio | X | X | X | X | X | X | X | |
| Coomb's Test (direct) | X | X | X | X | X | X | X | |
| hsCRP | | X | | X | | X | | |

Table 3: Treatment Period Procedural Outline After Week 24 (Protocol IM011021)

| Procedure | Week 28 D197 (±3 d) | Week 32 D225 (±3 d) | Week 36 D253 (±3 d) | Week 40 D281 (±3 d) | Week 44 D309 (±3 d) | Week 48 D337/EOT (±3 d) | FP (28 days after EOT) ^a | Notes |
|--|---------------------------|---------------------------|---------------------------|---------------------------|---------------------------|-------------------------------|---|---|
| TBNK | | X | | | | X | | |
| Serum Ig | | X | | | | X | X | IgM, IgA, IgG, IgE |
| PK Assessments | | X | | | | X | | See Section 8.6 |
| Biomarker Assessments | | | | | | | | |
| Serum Complement | X | X | X | X | X | X | X | C3, C4 |
| Anti-dsDNA autoantibodies | X | X | X | X | X | X | X | |
| | | | | | | | | |
| Blood RNA for IRG, steroid signature, and genome-wide expression | X | X | X | X | X | X | X | Assessment of IRG, steroid signature, and genome-wide expression; predose (Section 8.9) |

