3 OBJECTIVES AND ENDPOINTS

Table 4: Objectives and Endpoints

| Objectives | Endpoints |
|--|---|
| 
Primary Efficacy
 
 To assess the effect of BMS-986165 on the SRI(4) response at Week 32 in subjects with SLE | 
 Proportion of subjects who meet response criteria for SRI(4) (Section 8.1) at Week 32 |
| 
Secondary Efficacy
 
 To assess the effect of BMS-986165 on measures of global and organ-specific SLE clinical response | 
 Proportion of subjects who meet response criteria for SRI(4) at Week 48 Proportion of subjects who achieve a British Isles Lupus Assessment Group-based Composite Lupus Assessment (BICLA) response at Week 48 after treatment with BMS-986165 or placebo administered on stable background therapy (Section 9.3.1.1) Proportion of subjects who achieve Lupus Low Disease Activity State (LLDAS) at Week 48 (Section 8.1) Proportion of subjects with a Cutaneous Lupus Erythematosus Disease Area and Severity Index (CLASI) activity score ≥ 10 at baseline who achieve a CLASI response, defined as a decrease of $\geq 50\%$ from baseline CLASI activity score at Week 48 (Section 8.1) Change from baseline in the 40-joint count for tender, swollen, and tender + swollen joints at Week 48 |

Table 4: Objectives and Endpoints

| Objectives | Endpoints |
|---|---|
| 
Safety
 
 To assess the safety and tolerability of BMS-986165 | 
 Number and proportion of subjects experiencing serious adverse events (SAEs); AEs; and abnormalities in laboratory testing, vital signs, and electrocardiograms (ECGs) throughout the study |
| 
Pharmacokinetics
 
 To assess PK of BMS-986165 and its active metabolite (BMT-153261) in subjects with SLE (Section 8.6) | 
 Plasma concentration of BMS-986165 and BMT-153261 |

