6.7 Concomitant Therapy

All medications ever taken for SLE including topical, discontinued, and investigational therapies must be recorded; medications with dose changes may record the overall dates with last dose used. All medications taken from within 4 weeks before screening until 30 days after the last dose of study treatment (inclusive) must be recorded on the eCRF. Other than existing treatment for SLE (with restrictions as described in the eligibility criteria [[Section 5.1](#)]), concomitant medications (prescription, over-the-counter [OTC], or herbal) should only be administered during the study if they are prescribed for treatment of specific clinical events.

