7.3 Post Study Treatment Follow-Up

In this study, the proportion of subjects who achieve BICLA response at Week 32 after treatment with BMS-986165 or placebo is a key endpoint of the study. Post study follow-up is of critical importance and is essential to preserving subject safety and the integrity of the study. Subjects who discontinue study treatment must continue to be followed for collection of [REDACTED] survival follow-up data as required and in line with [Section 3](#) until death or the conclusion of the study.

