8.3.2 Time Period and Frequency for Collecting AE and SAE Information

The collection of nonserious AE information should begin at initiation of study treatment and continue until the last follow-up visit, at the timepoints specified in the Schedules of Activities ([Section 1.3](#)).

The Reference Safety Information in Sections 5.6.1 and 5.6.2 of the IB should be used to determine the expectedness of SAEs for expedited reporting. Following the subject's written consent to

participate in the study, all SAEs, whether related or not related to study treatment, must be collected, including those thought to be associated with protocol-specified procedures.

All SAEs that occur from the time the informed consent form (ICF) is signed through 30 days after the final dose of the study treatment must be reported to [REDACTED] Drug Safety. After that time, only SAEs deemed by the investigator to be related to the study treatment or a study procedure should be reported.

- The investigator must report any SAE that occurs after these time periods and that is believed to be related to study treatment or protocol-specified procedure. Medical occurrences that begin before the start of study treatment but after obtaining informed consent will be recorded on the appropriate section of the eCRF.
- All SAEs will be recorded and reported to Sponsor or designee within 24 hours, as indicated in [APPENDIX 3](#).
- The investigator will submit any updated SAE data to the Sponsor within 24 hours of this being available.

Investigators are not obligated to actively seek AEs or SAEs in former study subjects. However, if the investigator learns of any SAE, including a death, at any time after a subject has been discharged from the study, and he/she considers the event reasonably related to the study treatment or study participation, the investigator must promptly notify the Sponsor.

The method of evaluating and assessing causality of AEs and SAEs and the procedures for completing and reporting/transmitting SAE reports are provided in [APPENDIX 3](#).

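### Subjects who stop study drug stay in the study, but no off-treatment visits are defined, required medication and all-cause SAE records end 30 days after last dose, and SAP 7.2 leaves post-stop efficacy values out of the analysis visits

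*Protocol*

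**What the plan says.** **Staying in the study.** Protocol 7.1 rules that "Subjects who discontinue study treatment will remain in the study for continued follow-up". Sections 7.1 and 7.2 make exceptions only for withdrawn consent or loss of the ability to consent freely. On procedures, 7.1 says: "All subjects who discontinue study treatment should comply with protocol-specified follow-up procedures as outlined in" Section 1.3. Section 7.3 calls follow-up critical and requires it until death or the end of the study for survival data; part of the data type is blacked out. The reason it gives is that "the proportion of subjects who achieve BICLA response at Week 32" is a key endpoint.

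**The schedule.** In Table 3 of Section 1.3, EOT shares the Week 48 (Day 337) column. The only later column is "FP (28 days after EOT", for subjects not entering the extension study. It includes BILAG, SLEDAI-2K, the physician's global assessment, joint count and CLASI.

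**Record periods.** Section 6.7 sets the medication record "until 30 days after the last dose of study treatment (inclusive) must be recorded on the eCRF". Section 8.3.2 says all SAEs "through 30 days after the final dose of the study treatment must be reported", and later ones only if the investigator considers them related to treatment or a procedure. For other events: "The collection of nonserious AE information should begin at initiation of study treatment and continue until the last follow-up visit". The Table 4 safety endpoint counts SAEs, AEs and "abnormalities in laboratory testing, vital signs, and electrocardiograms (ECGs) throughout the study".

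**The analysis.** SAP 7.2 assigns efficacy measurements to analysis visits only when taken no later than last dose. In SAP 11.7.1, the primary analysis counts permanent IP discontinuation as non-response. Sensitivity #1 (treatment policy) counts only a missing value as non-response. Sensitivity #2 drops the medication rules but keeps IP discontinuation, missing values and study exit as non-response. SAP 11.7.2 repeats the sensitivity analyses for the secondary endpoints.

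**The concern.** The protocol keeps early stoppers in the study without saying which visits they attend. One site may do EOT and the 28-day visit and then stop; another may carry on to Week 48. Post-stop efficacy data would then exist for some subjects and not others, by site practice.

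The analysis that needs these data is sensitivity #1. It is meant to show whether the result survives when outcomes count regardless of stopping IP. If the values are never collected, or are collected and then left out by SAP 7.2, every such subject returns to non-response and the analysis no longer tests that question. Without a medication record, a response seen after stopping also cannot be read against any new SLE therapy.

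On safety, a retained subject's unrelated serious events would be reportable for a shorter time than nonserious events. That does not fit an endpoint that covers SAEs over the whole study.

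**Working it through.** No stated figure in the plan bears on this point, so there is none to reproduce. The check sets the collection rules against the SAP visit windows.

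**Inputs.** L = day of last dose, with EOT taken as that day (assumption). Post-treatment visit = L + 28 (Protocol Table 3). End of the required medication record and all-cause SAE reporting = L + 30 (Protocol 6.7, 8.3.2). Week 32 window: Days 212 to 239, target 225. Week 48 window: Days 324 to 351, target 337 (SAP 7.2).

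**Reading A: EOT at the stop, then the 28-day visit, then nothing.**
- Week 32: the 28-day visit falls in the window if 212 ≤ L + 28 ≤ 239, so L = 184 to 211. For L < 184 no assessment reaches the window.
- Week 48: 324 ≤ L + 28 ≤ 351, so L = 296 to 323. For L < 296 no assessment reaches the window.

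| Last dose (L) | 28-day visit | Records end | Days from visit to Day 225 | Days from records' end to Day 337 |
|---|---|---|---|---|
| 57 | 85 | 87 | 140 | 250 |
| 85 | 113 | 115 | 112 | 222 |
| 141 | 169 | 171 | 56 | 166 |
| 169 | 197 | 199 | 28 | 138 |

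**Reading B: the subject keeps attending scheduled visits.** Week 32 and Week 48 efficacy values are collected. The last column of the table is unchanged, because the two record periods run from last dose, not from the last visit. Nonserious AEs continue to the last follow-up visit, while SAEs judged unrelated stop being reportable at L + 30.

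**What SAP 7.2 does under either reading.** A value obtained after L is not assigned to an analysis visit. This covers all Reading B values and also the Reading A 28-day visits that fall inside a window, since L + 28 is later than L. In sensitivity #1 the subject then has no value at the visit and is a non-responder. Sensitivity #2 makes the same subject a non-responder for stopping IP. The two analyses can still differ for a subject assessed early in a window who stops shortly afterwards, so they come close rather than coincide.

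**What is untouched.** The primary analysis, and the secondary responder analyses modelled on it, make IP stoppers non-responders and use no post-stop value. The main joint-count model sets those visits to missing. Only its treatment-policy version needs them.

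**Section 7.3 against the endpoint list.** Section 7.3 names BICLA at Week 32. Table 4 and Section 9.3.1.1 list SRI(4) at Week 32 as primary and BICLA at Week 48 as secondary.

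**The case against.** The strongest reply is that nothing in the protocol ends visits after an early stop. Sections 7.1 to 7.3 say these subjects must continue to be followed, and EOT is printed as the Week 48 visit. SAP 11.7 plans efficacy listings to study end whatever the treatment status. That stands. A reader might infer that Week 32 and Week 48 outcomes are not collected; the documents do not support that, because the schedule is silent rather than prohibitive. Silence still leaves the choice to sites, and Protocol 9.3.5 points towards Reading A by tying database lock to completion or discontinuation plus the four-week safety follow-up.

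A reader might also infer that SAE reporting ends at 30 days, or that later deaths are lost. Neither holds. Related SAEs remain reportable, and 7.3 requires survival follow-up to study conclusion. The blacked-out words there may cover more, and they cannot be held against the plan. What lapses is required reporting of SAEs judged unrelated.

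Table 3 schedules concomitant medication at every visit, and 6.7 sets a minimum rather than forbidding later entries. Some sites may therefore record more, but nothing requires it. The planned AE summaries in SAP 11.8.1 stop 30 days after last dose anyway, so the loss is in the record and listings rather than in those tables.

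It could be argued that sensitivity #1 overrides SAP 7.2 by implication. No sentence says so, and the windowing rule is written without exception.

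**Conclusion.** The point holds in this form: off-treatment Week 32 and Week 48 efficacy values are not assured; required medication records and all-cause SAE reporting end 30 days after last dose even if visits continue; and SAP 7.2 as written keeps post-stop values out of the treatment-policy analyses. Sensitivity #1 then adds little to sensitivity #2. The primary conclusion is not at risk.

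The size can be given per subject only: for last doses on Days 57 to 169, between 250 and 138 days before Day 337 without a required medication or all-cause SAE record. The Day 184 and Day 296 limits assume that EOT is the last dose day and that visits stop after the 28-day visit.

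A headcount is tempting. If 15% to 25% stopped early, 14 to 23 of 90 per arm (0.15 × 90 = 13.5; 0.25 × 90 = 22.5) might seem to lack Week 48 outcomes. The documents give no discontinuation rate, and that count also assumes that nobody continues visits and nobody stops late. It should not be quoted as a finding.

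**What to change.** 1. **Protocol Table 3 and 7.3:** state that subjects who stop IP attend the remaining scheduled visits through Week 48 unless consent is withdrawn, with the existing efficacy instruments, corticosteroid dose and concomitant medication recorded.
2. **Protocol 6.7 and 8.3.2:** record medications and report all SAEs until the last study visit or 30 days after last dose, whichever is later.
3. **SAP 7.2 and 11.7.1:** exempt the treatment-policy analyses, including those of the secondary endpoints, from the last-dose limit on windowing. Without this step, the extra visits would not reach the analysis that needs them.
4. **Protocol 7.3:** replace BICLA at Week 32 with the current endpoints, SRI(4) at Week 32 and the Week 48 secondaries.

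The cost is a protocol amendment, a SAP revision and extra visits for early stoppers, some of whom will decline. No new instrument or visit type is needed, and no treatment rule changes.

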7.2 Discontinuation from the Study

Subjects who request to discontinue study treatment (possible circumstances are listed in [Section 7.1](#)) will remain in the study and must continue to be followed for protocol-specified follow-up procedures. The only exception to this is when a subject specifically withdraws consent for any further contact with him/her or persons previously authorized by subject to provide this information.

- Subjects should notify the investigator of the decision to withdraw consent from future follow-up **in writing**, whenever possible.
- The withdrawal of consent should be explained in detail in the medical records by the investigator and entered on the appropriate eCRF page.
- In the event that vital status (whether the subject is alive or dead) is being measured, publicly available information should be used to determine vital status only as appropriately directed in accordance with local law.
- If the subject withdraws consent for disclosure of future information, the Sponsor may retain and continue to use any data collected before such a withdrawal of consent.

7.3 Post Study Treatment Follow-Up

In this study, the proportion of subjects who achieve BICLA response at Week 32 after treatment with BMS-986165 or placebo is a key endpoint of the study. Post study follow-up is of critical importance and is essential to preserving subject safety and the integrity of the study. Subjects who discontinue study treatment must continue to be followed for collection of [REDACTED] survival follow-up data as required and in line with [Section 3](#) until death or the conclusion of the study.

7.4 Lost to Follow-Up

- All reasonable efforts must be made to locate subjects to determine and report their ongoing status. This includes follow-up with persons authorized by the subject.
- Lost to follow-up is defined by the inability to reach the subject after a minimum of 3 documented phone calls, faxes, or emails as well as lack of response by subject to 1 registered mail letter. All attempts should be documented in the subject's medical records.
- If it is determined that the subject has died, the site will use permissible local methods to obtain date and cause of death.
- If investigator's use of third-party representative to assist in the follow-up portion of the study has been included in the subject's informed consent, then the investigator may use a Sponsor retained third-party representative to assist site staff with obtaining subject's contact information or other public vital status data necessary to complete the follow-up portion of the study.
- The site staff and representative will consult publicly available sources, such as public health registries and databases, to obtain updated contact information.
- If after all attempts, the subject remains lost to follow-up, then the last known alive date as determined by the investigator should be reported and documented in the subject's medical records.

7.5 Replacement of Subjects

Subject replacement is not permitted.

8 STUDY ASSESSMENTS AND PROCEDURES

Study procedures and timing are summarized in the Schedules of Activities ([Section 1.3](#)). Waivers or exemptions from protocol-required evaluations are not allowed.

8.1 Efficacy Assessments

Protocol-specific training and assessments must be successfully completed so that investigators or designees can be qualified to perform assessments using the BILAG, CLASI, SLEDAI-2K, and 40-joint count tools. Every effort must be made to ensure that the same evaluator(s) complete the assessment for each subject. If the evaluator(s) is unable to complete the evaluation, then a qualified individual with overlapping experience may perform the evaluation. Documentation of who performed the evaluation is to be recorded in source documents. Assessments are to be performed at approximately the same time of day throughout the duration of the study.

Baseline assessments must be performed per protocol (standard of care assessments may not be used for baseline). Procedures not specified in the protocol that are part of standard care may be performed if they do not interfere with study procedures; any data arising from such procedures are not to be reported in the eCRF.

Note: NSAIDs must be withheld for at least 12 hours before visits at which BILAG, SLEDAI-2K, joint counts, CLASI, or Physician's Global Assessment of Disease Activity are assessed (ie, all scheduled visits). Study treatment must not be taken on visit days until after efficacy assessments.

The following procedures or tools will be used to assess subjects' SLE disease activity during the study (see schedule in [Section 1.3](#)):

- BILAG-2004^{10, 11, 12, 13} ([APPENDIX 10](#)): The BILAG-2004 rating is based on organ systems (constitutional, mucocutaneous, neuropsychiatric, musculoskeletal, cardiorespiratory, gastrointestinal, ophthalmic, renal, and hematological). Each is scored by a number of assessments, from which an overall grade is derived for each organ system. The overall grades are represented as 5 different levels from A to E (A = very active, B = moderate disease activity, C = mild stable disease, D = no disease activity but suggests the system had previously been affected, and E = no current or previous disease activity).
- SLEDAI-2K^{14,15} ([APPENDIX 11](#)): The SLEDAI-2K is a global index based on weighted scores for each of 24 clinical findings rated as present or absent at the time of the visit or in the last 30 days. The SLEDAI-2K assigns relative weights to each parameter.
- CLASI^{16,17} ([APPENDIX 12](#)): The CLASI assesses cutaneous disease activity by body surface area; points are given for presence of erythema, scale, hypertrophy, mucous membrane lesions, recent hair loss, and physician-observed alopecia. For the damage assessments, points are given for dyspigmentation, scarring, and scarring alopecia.
- 40-joint count: A 40-joint count is used. This includes bilateral wrists, elbows, ankles, knees, interphalangeal joints of the thumb, individual proximal interphalangeal joints of the hand, second through fifth metacarpophalangeal joints of the hand, and individual metatarsophalangeal joints of the feet (which make up the 36-joint count).^{18, 19, 20} To allow the 28-joint count evaluation, bilateral first metacarpophalangeal joints and shoulders are also included, bringing the total joint count to 40. Each joint is evaluated based upon the presence or absence of tenderness, the presence or absence of swelling, and the presence or absence of both tenderness and swelling.
- Physician's Global Assessment of Disease Activity assessed using a 3-point visual analog scale (VAS).

The following composite measures will be determined based on some of the assessments described above:

- BICLA response²¹ as defined in [Section 9.3.1.1](#)

- SLE Responder Index²² (SRI): The SRI is a composite endpoint that defines a responder as a patient whose disease course fulfills all of the following:
 - A predefined reduction (number of points) from baseline in SLEDAI-2K score^{14,15} (APPENDIX 11). The SRI can be calculated based on the number of points of reduction in the SLEDAI-2K (SRI[4], SRI[5], SRI[6], and SRI[7]).
 - No new BILAG A (severe disease activity) or not more than 1 new BILAG B (moderate disease activity) organ domain grade
 - No worsening from baseline in the Physician's Global Assessment of Disease Activity scale by more than 0.3 points
- Lupus Low Disease Activity State (LLDAS):^{23,24} LLDAS is defined as follows: (1) SLEDAI-2K ≤ 4 , with no activity in major organ systems (renal, central nervous system, cardiopulmonary, vasculitis, fever) and no hemolytic anemia or gastrointestinal activity (measured as maintaining a D or E score in the BILAG Gastrointestinal Body System); (2) no new lupus disease activity compared with the previous assessment measured as no new or worsening individual BILAG parameters; (3) Physician's Global Assessment of Disease Activity ≤ 1 ; (4) a current prednisolone (or equivalent) dose ≤ 7.5 mg daily; and (5) well-tolerated standard maintenance doses of immunosuppressive drugs and approved biological agents.

